#### **8.4.3.3 Home peak expiratory flow (morning and evening)**

Changes from baseline in morning and evening PEF up to Week 52 will be calculated.

#### **8.4.3.4 Asthma Control Questionnaire (ACQ-6)**

In the ACQ-6 questionnaire the subjects are asked to recall the status of their asthma during the previous week with regards to symptom, use of short acting  $\beta$ -agonists and BD. The questionnaire includes questions on

1. Awoken at night by symptoms
2. Limitation of normal daily activities
3. Waking in the morning with symptoms
4. Dyspnoea
5. Wheeze
6. Daily rescue medication

The questions of the ACQ-6 are measured on a 7-point scale scored from 0 (totally controlled) to 6 (severely uncontrolled). The ACQ-6 score is computed as the un-weighted mean of the responses.

Other variables based on ACQ-6 to report include:

- ACQ-6-responder (Yes=1/No=0)
  - Responder: Change from baseline ACQ-6 score  $\leq -0.5$
  - Non-responder : Change from baseline ACQ-6 score  $> -0.5$
- ACQ-6-responder (improved/No Change / Deterioration)
  - Improvement: Change from baseline ACQ-6 score  $\leq -0.5$

- No change:  $-0.5 < \text{Change from baseline ACQ-6 score} < 0.5$
- Deterioration:  $\text{Change from baseline ACQ-6 score} \geq 0.5$
- Subjects asthma control as measured by ACQ-6 score:
  - Well controlled :  $\text{ACQ-6 score} \leq 0.75$
  - Partly controlled :  $0.75 < \text{ACQ-6 score} < 1.5$
  - Not well controlled :  $\text{ACQ-6 score} \geq 1.5$

#### **8.4.3.5 Asthma quality of life questionnaire for 12 years and older (AQLQ(S) +12)**

The AQLQ(S)+12 will be first completed at Visit 3 (Week 0), which will be used as the baseline assessment. Subjects are asked to recall their experiences during the previous 2 weeks and to score each of the 32 questions on a 7-point scale ranging from 7 (no impairment) to 1 (severe impairment).

The overall score is calculated as the mean response to all questions. The 4 individual domain scores (4 domains assessing 1) symptoms, 2) activity limitations, 3) emotional function, and 4) environmental stimuli) are the means of the responses to the questions in each of the domains.

The key outcome variable for the AQLQ(S)+12 will be the change in mean score from baseline to each of the post-randomization periods. The change from baseline will be derived as post-randomization score minus baseline score, there will be no imputation for missing values.

Other variables based on AQLQ(S) +12 to be reported include:

- AQLQ(S) +12 -responder (Yes=1/No=0)
  - Responder:  $\text{Change from baseline AQLQ(S) +12 score} \geq 0.5$
  - Non-responder :  $\text{Change from baseline AQLQ(S) +12 score} < 0.5$
- AQLQ(S) +12 -responder (improved/No Change / Deterioration)
  - Improvement:  $\text{Change from baseline AQLQ(S) +12 score} \geq 0.5$
  - No change:  $-0.5 < \text{Change from baseline AQLQ(S) +12 score} < 0.5$
  - Deterioration:  $\text{Change from baseline AQLQ(S) +12 score} \leq -0.5$

#### **8.4.3.6 European quality of life-5 dimensions-5 levels (EQ-5D-5L)**

The questionnaire assesses 5 dimensions: mobility, self-care, usual activities, pain/discomfort and anxiety/depression. Each dimension has 5 response options (no problems, slight problems, moderate problems, severe problems, and extreme problems) that reflect increasing levels of difficulty.

The subject will be asked to indicate his/her current health state by selecting the most appropriate level in each of the 5 dimensions. The questionnaire also includes a visual analogue scale, where the subject will be asked to rate current health status on a scale of 0-100, with 0 being the worst imaginable health state.

The change from baseline in visual analogue scale will be calculated by visit.

#### **8.4.3.7 Health care resource utilization**

Broad-based health care utilization event information will be collected by the Investigator/authorized delegate at each visit as specified in the protocol and recorded in the appropriate eCRF module. Examples include aspects such as unscheduled physician visits or telephone calls or ambulance transport.

#### **8.4.3.8 The Work Productivity and Activity Impairment Questionnaire plus Classroom Impairment Questions (WPAI+CIQ)**

The Work Productivity and Activity Impairment Questionnaire plus Classroom Impairment Questions (WPAI+CIQ) will be first completed at Visit 3 (Week 0), which will be used as the baseline assessment.

The WPAI+CIQ questionnaire is a 10-item questionnaire that assesses productivity and activity impairment over the previous week.

There are a maximum of 10 questions and a minimum of 3 questions that will be completed by subjects as follows:

1. Currently employed (yes/no)
2. Hours missed work due to health problems
3. Hours missed work due to other reasons
4. Hours actually worked
5. Degree health affected productivity while working (0-10 scale, with 0 meaning no effect)
6. Attends class in an academic setting (yes/no)
7. Hours missed class due to health problems
8. Hours actually attended class
9. Degree health affected productivity while attending class (0-10 scale, with 0 meaning no effect)
10. Degree health affected regular activities (other than work or class) (0-10 scale, with 0 meaning no effect)

If the answer to question 1 is 'No, not currently employed', then the subject should skip to question 6. If the answer to question 6 is 'No, not currently attending class', then the subject should skip to question 10.

The WPAI+CIQ provide 4 scores:

- Absenteeism (work or class time missed),
- Presenteeism (impairment at work or class/reduced on-the-job effectiveness),
- Work productivity loss (overall work or class impairment/absenteeism plus presenteeism)

- Activity impairment.

WPAI+CIQ outcomes are expressed as impairment percentages, with higher numbers indicating greater impairment and less productivity.

For the work related questions, the following calculations should be used to create the outcomes of interest:

- Absenteeism =  $Q2/(Q2+Q4)$
- Presenteeism =  $Q5/10$
- Work Productivity Loss =  $Q2/(Q2+Q4)+[(1-Q2/(Q2+Q4))x(Q5/10)]$
- Activity Impairment =  $Q10/10$

The class related questions will be used in a similar manner.

#### 8.4.4 Calculation or derivation of safety variable(s)

The following safety data will be collected: vital signs, physical examination, 12-lead dECG, hematology, clinical chemistry, urinalysis, and reported AEs.

Change from baseline (Visit 3) to each post-baseline time point where scheduled assessments were made will be calculated for relevant measurements.

##### 8.4.4.1 Adverse events

Adverse events experienced by the subjects will be collected throughout the entire study and will be coded by the AstraZeneca designee using the latest version of the Medical Dictionary for Regulatory Activities (MedDRA).

AE data will be categorized according to their onset date into the following study periods:

- AEs occurring during run-in (onset date  $\geq$  Visit 1 and before the first dose of study treatment)
- AEs occurring during treatment (onset date  $\geq$  the first day of study treatment and  $\leq$  the last day of study treatment + 2 weeks)
- AEs occurring during follow-up, consisting of AE with
  - onset date  $>$  the last day of study treatment + 2 weeks and  $\leq$  date of week 72; this is only applicable for subjects that are treated for the entire treatment period
  - onset date  $>$  the last day of study treatment + 2 weeks and  $\leq$  the last day of study treatment + 22 weeks ; this is only applicable for subjects that prematurely discontinued treatment

- AEs occurring post-treatment (onset date > the last day of study treatment + 22 weeks; this is only applicable for subjects that prematurely discontinued treatment)

The timing of AEs will be assigned to the period in which they first occurred. If an AE has a missing onset date, then unless the stop date of the AE indicates otherwise, this will be considered an on treatment event. Similarly, if an AE has a partial onset date, then unless the partial onset date or the stop date indicates otherwise, this will be considered an on treatment AE.

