### **6.1 Definition of adverse events**

An AE is the development of an undesirable medical condition or the deterioration of a pre-existing medical condition following or during exposure to a pharmaceutical product, whether or not considered causally related to the product. An undesirable medical condition can be symptoms (e.g., nausea, chest pain), signs (e.g., tachycardia, enlarged liver) or the abnormal results of an investigation (e.g., laboratory findings, electrocardiogram). In clinical studies, an AE can include an undesirable medical condition occurring at any time, including run-in or washout periods, even if no study treatment has been administered.

The term AE is used to include both serious and non-serious AEs.

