#### **6.3.3 Adverse event variables**

The following variables will be collected in the eCRF for each AE:

- AE (verbatim)
- The date when the AE started and stopped
- Maximum intensity\* of the AE
- Whether the AE is serious or not
- Investigator causality rating against the Investigational Product (yes or no)
- Action taken with regard to IP
- AE caused subject's withdrawal from study (yes or no)
- Outcome

\*Intensity rating scale:

- 1 mild (awareness of sign or symptom, but easily tolerated)
- 2 moderate (discomfort sufficient to cause interference with normal activities)

- 3 severe (incapacitating, with inability to perform normal activities)

In addition, the following variables (if applicable) will be collected in the eCRF for SAEs:

- Date AE met criteria of serious
- Date Investigator became aware of the SAE
- AE is serious due to
- Date of hospitalization
- Date of discharge
- Probable cause of death
- Date of death
- Autopsy performed
- Causality assessment in relation to Study procedure(s)
- Description of the AE

It is important to distinguish between serious and severe AEs. Severity is a measure of intensity, whereas seriousness is defined by the criteria in Section 6.2. An AE of severe intensity need not necessarily be considered serious. For example, nausea that persists for several hours may be considered severe nausea, but not a SAE unless it meets the criteria shown in Section 6.2. On the other hand, a stroke that results in only a limited degree of disability may be considered a mild stroke but would be a SAE when it satisfies the criteria shown in Section 6.2.

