#### **8.5.8.1 Adverse events**

AEs will be summarized separately for the treatment and follow-up periods, as defined in Section 6.3. AEs occurring during the run-in period, or occurring post-treatment (as per the definition above) will be listed, but not summarized.

An overall summary table will be produced showing the number and percentage of subjects with at least 1 AE in any of the following categories; AEs, SAEs, deaths due to AE, DAEs, and other significant adverse events (OAEs). The total number of AEs in the different AE categories in terms of AE counts will also be presented (i.e., accounting for multiple occurrences of the same event in a subject).

AEs will be summarized by SOC and PT assigned to the event using MedDRA. For each PT, the number and percentage of subjects reporting at least one occurrence will be presented i.e., for a subject multiple occurrences of an AE will only be counted once.

AEs (by PT) will be summarized by causality and maximum intensity. If a subject reports multiple occurrences of the same AE, the maximum intensity will be taken as the highest recorded maximum intensity (the order being mild, moderate, and severe). SAEs, OAEs, DAEs, and deaths will also be summarized in separate tables.

The rate of AEs per person-years at risk, calculated as (number of subjects reporting AE)/(total time at risk of AE), will also be reported. Rates will typically be expressed in terms of events per 100 subject-years.

Separate listings of subjects with AEs, SAEs, death due to AE, or discontinuations due to AEs will be presented.

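### An AE that starts in run-in and turns serious, turns fatal or stops IP after dosing is left out of the AE summary tables unless the site opens a new record

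*Protocol*

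**What the plan says.** Protocol 8.4.4.1 sorts AEs on one variable: "AE data will be categorized according to their onset date into the following study periods". Run-in covers onset from Visit 1 until just before the first dose. Treatment runs from the first dose to two weeks after the last, and follow-up comes after that. For an event that spans periods the rule is "The timing of AEs will be assigned to the period in which they first occurred".

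Protocol 8.5.8.1 says which periods are tabulated: "AEs will be summarized separately for the treatment and follow-up periods, as defined in Section 6.3". It also says "AEs occurring during the run-in period, or occurring post-treatment (as per the definition above) will be listed, but not summarized". On the tables of most interest it adds only that "SAEs, OAEs, DAEs, and deaths will also be summarized in separate tables".

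Protocol 6.1 sets the scope of the term: "The term AE is used to include both serious and non-serious AEs". Protocol 6.3.3 collects, for each AE, "The date when the AE started and stopped", a single maximum intensity and the action taken with IP. For SAEs it also collects "Date AE met criteria of serious" and the date of death.

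**The concern.** A condition already present at the first dose that worsens on study drug is something treatment-period safety tables should show. The data collection allows for it, because the date of becoming serious is kept apart from the date of onset. The period rule does not use that second date. If one record starts before dosing and turns serious afterwards, the rule looks back to the start and sends it to a period that is not tabulated.

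At stake are the counts of SAEs, deaths and discontinuations due to AE by arm. These counts are usually low, so one or two omitted events can be noticeable.

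**Working it through.** No formula applies. The check reads the rules together and follows one case through them.

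1. **Which rule governs.** 8.5.8.1 refers to Section 6.3 for the periods, but 6.3.1 only says how long AEs are collected (consent to Week 72). Only 8.4.4.1 divides AEs into run-in, treatment, follow-up and post-treatment, so it is the operative rule.
2. **Whether it covers serious events.** By 6.1 the term AE includes SAEs. 8.5.8.1 gives the SAE, DAE and death tables no separate date rule, so the onset rule applies to them too.
3. **Constructed case.** A mild AE starts on Day -6. The first dose is on Day 1. The AE leads to hospital admission on Day 10, and IP is stopped. Onset precedes the first dose, so 8.4.4.1 makes it a run-in AE, and 8.5.8.1 lists it without summarizing it.
4. **Where the case appears.**
   - Absent: the overall AE summary, the tables by SOC and PT, the causality and intensity tables, and the SAE and DAE tables. Had it been fatal, it would also be absent from the death table.
   - Present: the separate listings in 8.5.8.1 and, because IP was stopped, the disposition table in 8.5.3, which counts treatment discontinuations by reason.
5. **Internal consistency.** The abbreviation list defines a DAE as stopping IP because of an AE. IP cannot be stopped before it is started, so every DAE takes effect on or after the first dose. The onset rule still drops a DAE whose AE began earlier. The same subject is then a discontinuation in 8.5.3 and missing from the DAE table in 8.5.8.1.
6. **Contrast within 8.4.4.1.** An AE with a missing onset date counts as on treatment by default. An AE with a known pre-dose onset and a known on-treatment serious date does not. The inclusive default stops where the information is better.

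**Scale, as illustration only.** The protocol gives no AE rates. Suppose 15% to 30% of 770 subjects have a run-in AE, 20% to 40% of those AEs are ongoing at the first dose, and 1% to 3% of these turn serious on treatment. None of these percentages comes from the document.
- Low end: 770 × 0.15 × 0.20 = 23 subjects; 23 × 0.01 = 0.2 events.
- High end: 770 × 0.30 × 0.40 = 92 subjects; 92 × 0.03 = 2.8 events.

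These are totals over both arms and do not count AEs that stop IP without being serious. They also ignore the screening rules discussed under the objection, which would lower them.

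**The case against.** A reader might infer that these events disappear from safety reporting. The protocol does not support that. 8.5.8.1 requires listings of subjects with AEs, SAEs, deaths due to AE and discontinuations due to AE. 8.5.3 counts stopping of treatment. Section 6.4 requires SAE reports within 24 hours, and 6.8.1 sends all hospitalizations and deaths to blinded adjudication. The gap is in the AE summary tables only.

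The strongest counter-argument is that 6.1 treats worsening of an existing condition as an AE in itself, and 6.3.6 requires clinically relevant aggravated examination findings to be reported as AEs. A site could therefore open a new record with an on-treatment onset, and that record would be summarized. This stands as a mitigation. For worsening in general, however, no instruction requires a new record, and a single maximum intensity with a separate serious date permits one continuous record. The table counts would then depend on site habit.

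Screening also thins the affected group. Exclusion criteria 2, 6, 8 and 15 in 3.2 remove unstable disorders, treated infections, risky run-in findings and significant exacerbations, and 7.2 postpones dosing during intercurrent illness that may compromise safety. This supports a small number, but not zero.

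Finally, onset-based assignment is an ordinary convention, and the SAP, not available here, may add a worsening rule. That is fair. But the protocol states its rule outright, and the rule as stated produces the gap.

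**Conclusion.** The point holds for AE summary tables, for AEs kept on a single record with pre-dose onset. It follows from 8.4.4.1 and 8.5.8.1 read together and does not depend on any assumed rate. The number of events cannot be derived from the protocol and is probably small; the 0.2 to 2.8 range shows scale under invented inputs and is not an estimate.

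A reader might also infer that the rule biases the comparison between arms. The documents give no basis for a direction: the rule is the same in both arms, and either could lose events. Efficacy is unaffected. What remains is possible understatement of on-treatment SAEs and deaths, and a DAE table that need not agree with disposition. That is a modest defect, worth correcting because the events concerned are serious and the correction is cheap.

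**What to change.** Add one sentence to 8.4.4.1, limited to AEs with onset before the first dose. Suggested sense: if such an AE meets serious criteria, leads to discontinuation of IP or results in death on or after the first dose, it is also summarized in the period containing that date, in the overall AE summary as well as in the SAE, DAE and death tables. Including the overall summary keeps an event from counting as an SAE but not as an AE. Saying before the first dose, rather than run-in, also covers onset between consent and Visit 1, which 8.4.4.1 assigns to no period.

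Leave onset-based assignment unchanged for AEs with onset on or after the first dose. Reassigning every SAE, DAE and death by its later date would do harm. An AE with on-treatment onset that turns serious in follow-up would leave the treatment-period table. In a subject who stopped IP early, a death more than 22 weeks after the last dose could move into the post-treatment period, which is not summarized.

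The cost is one sentence and a small programming change. Dates of seriousness and death (6.3.3) and of IP administration (7.5) are already collected. On-treatment SAE and DAE counts may be slightly higher in both arms. Worsening that is neither serious nor fatal and does not stop IP would stay in the listings only.

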#### **8.4.4.2 Other significant adverse events**

During the evaluation of the AE data, an AstraZeneca medically qualified expert will review the list of AEs that were not reported as SAEs or discontinuations due to AEs.

Based on the expert's judgment, significant AEs of particular clinical importance may, after consultation with the Global Patient Safety Physician, be considered other significant AEs (OAEs) and reported as such in the CSR.

Examples of these are marked hematological and other laboratory abnormalities, and certain events that led to intervention (other than those already classified as serious), dose reduction, or significant additional treatment.

#### **8.4.4.3 Laboratory variables**

Blood and urine samples for determination of clinical chemistry, haematology and urinalysis parameters will be taken at the times detailed in the CSP, and will be assessed in a central laboratory. The parameters outlined in [Table 2](#), [Table 3](#), [Table 4](#) and [Table 5](#) in Section [5.1.6.1](#), will be collected. Laboratory data will be reported in SI units.

Changes in haematology and clinical chemistry variables between baseline and each subsequent scheduled assessment will be calculated. Baseline is defined as the last available value measured prior to the first dose of randomized treatment. The change from baseline is defined as the treatment period value minus the baseline period value. There will be no imputation for missing values.

Absolute values will be compared to the relevant reference range and classified as low (below range), normal (within range or on limits) or high (above range). The AstraZeneca extended reference ranges will be used for laboratory variables (where they exist). All values (absolute and change) falling outside the reference ranges will be flagged.

Urinalysis data will be categorised as negative (0), trace or positive (+) at each time-point.

For the purposes of haematology, clinical chemistry and urinalysis shift tables, baseline will be defined as the latest non-missing assessment prior to first dose, and on-treatment will be defined as the latest non-missing assessment whilst the subject is ongoing on treatment.

For the liver function tests: AST, ALT, ALP, GGT and total bilirubin, the multiple of the AstraZeneca ULN (not extended) range will be calculated for each data point.

$$\text{Multiple} = \text{Value} / \text{ULN}$$

i.e., if the ALT value was 72 IU/L (ULN 36) then the multiple would be 2.

Subjects who meet any of the following criteria at any point during the study will be flagged:

$$\text{Multiple} = \text{Value} / \text{ULN}$$

i.e., if the ALT value was 72 IU/L (ULN 36) then the multiple would be 2.

Subjects who meet any of the following criteria at any point during the study will be flagged:

- $\text{AST} \geq 3x \text{ ULN}$
- $\text{ALT} \geq 3x \text{ ULN}$
- $\text{TBL} \geq 2x \text{ ULN}$

#### 8.4.4.4 dECGs

Twelve-lead dECG measurements will be recorded in accordance with the protocol, with the baseline visit being defined as Visit 1.

The outcome of the overall evaluation is to be recorded as normal/abnormal in the eCRF, with any abnormalities being recorded as not clinically significant or clinically significant.

#### 8.4.4.5 Physical examination

Complete and brief physical examinations will be performed at time points specified in [Table 1](#). What is included in the assessment will be dependent on whether the examination is complete or brief, as described in [Section 5.1.7](#). For the brief physical examination, only information on whether the assessment was performed or not will be recorded.

Each component of the baseline visit (i.e., Visit 3) complete physical examination will be recorded as normal or abnormal. Each component of the follow-up complete physical examinations will be recorded as normal, same as baseline, or new/aggravated.

Any new finding(s), or aggravated existing finding(s), judged as clinically significant by the Investigator, will be reported as an AE.

